14.1.36 Incomplete dates for last known date patient alive or death

All dates must be completed with day, month and year. If the day is missing, the 15th of the month will be used for incomplete death dates or dates of last contact.

14.1.37 Non-target lesion response

If no non-target lesions are identified at baseline (and therefore not followed throughout the study), the non-target lesion response at each assessment will be considered 'not applicable (NA)'.

14.1.38 Study/project specific programming

The standard analysis programs need to be adapted for each study/project.

14.1.39 Censoring reason

In order to summarize the various reasons for censoring, the following categories will be calculated for each time to event variable based on the treatment completion page, the study evaluation completion page and the survival page.

For survival the following censoring reasons are possible:

- Alive
- Lost to follow-up

For PFS and TTP (and therefore duration of responses) the following censoring reasons are possible:

- Ongoing without event
- Lost to follow-up
- Withdraw consent
- Adequate assessment no longer available*
- Event documented after two or more missing tumor assessments (optional, see [Table 14-5](#))
- Death due to reason other than underlying cancer (*only used for TTP and duration of response*)
- Initiation of new anti-cancer therapy

*Adequate assessment is defined in [Section 14.1.25](#). This reason is applicable when adequate evaluations are missing for a specified period prior to data cut-off (or prior to any other censoring reason) corresponding to the unavailability of two or more planned tumor assessments prior to the cut-off date. The following clarifications concerning this reason should also be noted:

- This may be when there has been a definite decision to stop evaluation (e.g. reason="Sponsor decision" on study evaluation completion page), when patients are not followed for progression after treatment completion or when only UNK assessments are available just prior to data cut-off).
- The reason "Adequate assessment no longer available" also prevails in situations when another censoring reason (e.g. withdrawal of consent, loss to follow-up or alternative anti-cancer therapy) has occurred more than the specified period following the last adequate assessment.
- This reason will also be used to censor in case of no baseline assessment.

All tumor lesions/lymph nodes will be categorized as measurable or non-measurable as follows:

a. Measurable Nodal and extranodal lesions

A lesion will be called **measurable** if it can be measured accurately in 2 perpendicular dimensions and:

- For nodal lesion, if the long axis is > 15 mm, regardless of the length of the short axis,
- For extranodal lesion, if the long and short axes are ≥ 10 mm.

Patients should have **at least one measurable nodal lesion greater than 20 mm** in the long axis.

In cases where the patient has no measurable nodal lesions greater than 20 mm in the long axis at Screening, then the patient must have at least one measurable extranodal lesion

b. Classification of lymph nodes

Lymph nodes are classified according to their size and/or relationship to the disease:

- A lymph node meeting the measurability requirement above will constitute a **measurable nodal lesion**.
- A lymph node not meeting the measurability requirement but with long axis ≥ 15 mm (e.g. short axis cannot be measured accurately) will constitute a **non-measurable nodal lesion**.
- A lymph node not meeting the measurability criteria but with a size of 11 mm to 15 mm in the long axis and ≥ 10 mm in the short axis will be checked for relationship to disease:
 - If it is thought to be disease related, it will constitute a **non-measurable nodal lesion**
 - If it is not thought to be disease related, it will constitute an **abnormal lymph node** but not a lesion.
- All other lymph nodes will be considered normal and will not constitute nodal lesions.

c. Criteria for normalization of lesions

The normalization of lesions is defined as follow:

- A measurable nodal lesion must become ≤ 15 mm in long axis to be considered normalized.
- A non-measurable nodal lesion must decrease to ≤ 10 mm in the short axis and be ≤ 15 mm in long axis to be considered normalized.
- An extranodal lesion must disappear completely (assigned a size of 0 mm x 0 mm) to be considered normalized.

3 Specification by methods of measurement

a. Measurement of lesions

All radiological measurements should be taken in two perpendicular dimensions and recorded in metric notation, using a ruler or calipers.

i. PET

Visual assessment currently is considered adequate for determining whether a PET scan is positive, and use of the standardized uptake value is not necessary.¹ In brief, a positive scan is defined as focal or diffuse FDG uptake above background in a location incompatible with

normal anatomy or physiology, without a specific standardized uptake value cutoff.¹ Other causes of false-positive scans should be ruled out. Exceptions include mild and diffusely increased FDG uptake at the site of moderate- or large-sized masses with an intensity that is lower than or equal to the mediastinal blood pool, hepatic or splenic nodules 1.5 cm with FDG uptake lower than the surrounding liver/spleen

ii. CT scan (or MRI)

For optimal evaluation of patients, the same methods of assessment and technique should be used to characterize each identified and reported lesion at Screening and during follow-up. Contrast-enhanced CT of chest, abdomen and pelvis should preferably be performed using a 5mm slice thickness with a contiguous reconstruction algorithm. CT/MRI scan slice thickness should not exceed 8 mm cuts using a contiguous reconstruction algorithm. If at Screening a patient is known to be allergic to CT contrast or develops allergy during the trial, the following change in imaging modality will be accepted for follow up: a non-contrast CT of chest (MRI not recommended due to respiratory artifacts) plus contrast-enhanced MRI of abdomen and pelvis.

A change in methodology can be defined as either a change in contrast use (e.g. keeping the same technique, like CT, but switching from with to without contrast use or vice-versa, regardless of the justification for the change) or a change in technique (e.g. from CT to MRI, or vice-versa), or a change in any other imaging modality. A change in methodology will result by default in an “Unknown” overall radiological response assessment. However, another overall radiological response than the Novartis calculated “Unknown” response may be accepted from the investigator if a definitive overall radiological response can be justified to be based on the available information.

In order to calculate the sum of the product of the diameters (SPD) of all index lesions (or extranodal lesions), their size must be entered throughout the study.

Actual lesion measurements should be entered on the corresponding eCRFs. If, during the course of the study, either of the perpendicular diameters of a lesion cannot be reliably measured because of its small size, it is recommended to enter the minimum limit of detection as the diameter size (e.g. 5 mm for spiral CT). In other cases when, during the course of the study, the diameter cannot be reliably measured for reasons other than its size (i.e. borders of the lesion are confounded by neighboring anatomical structures), no measurement should be entered and the lesion cannot be evaluated.

If lesions become confluent over time, it is recommended to measure them as one lesion, report the overall diameters to one of the lesions and assign 0 mm x 0 mm to each of the other previously measured lesions. If a lesion splits during the study, each sub-lesion should be measured separately for all subsequent assessments and all sub-lesions contribute to the SPD.

iii. Bone marrow assessment

Documentation of status of bone marrow involvement by lymphoma based on prior bone marrow biopsy or aspirate findings is required at Screening for all patients.

If no such documentation is available then a bone marrow biopsy or aspirate should be performed at Screening.

If bone marrow involvement is assessed by biopsy, the biopsy sample should have a goal of > 20 mm unilateral core. If the biopsy sample is indeterminate by morphology (immunohistochemistry), then flow cytometry may be performed on bone marrow aspirate to confirm the findings.

iv. Physical examination and assessment of B-symptoms

Skin lesions, if the size is ≥ 20 mm in at least one diameter, must be histologically confirmed for lymphoma involvement (the investigational site must document the histological confirmation (yes or no) on the corresponding eCRF) and photographed including a ruler (color photography using digital camera). Tumor assessment will be performed and results will be recorded on the corresponding eCRF at Screening and at Day 1 of every cycle (± 4 days) after first dose of study drug.

B-symptoms are of importance in determining prognosis and should resolve completely in patients who have achieved complete response. B-symptoms in lymphoma patients are disease related clinical symptoms and are not caused by anticancer therapy (or drug toxicity).

B-symptoms are defined as follows:

- Significant unexplained fever ($\geq 38^{\circ}\text{C}$),
- Unexplained, recurrent drenching night sweats
- Unexplained loss of $> 10\%$ body weight within the previous 6 months, as assessed and reported (present vs. absent) by the Investigator.

4. Evaluation of Radiological Response

For the sake of simplicity, complete remission and complete response will both be referred to as complete response.

Definitions of Response for Lymphoma patients are listed in [Table 4-1](#). To evaluate disease response to treatment, all index and non-index lesions will be followed and assessed throughout the study. At each assessment, response is evaluated separately for the **index lesions** ([Table 4-1](#)) and **non-index lesions** ([Table 4-2](#)) identified at Screening, then a combined overall radiological response is determined ([Table 4-3](#)).

Table 4-1 Response Definition for Lymphoma

Response	Definition	Nodal Masses	Spleen. Liver	Bone Marrow
CR	Disappearance of all evidence of disease	a FDG-avid or PET positive prior to therapy; mass of any size permitted if PET negative b Variably FDG-avid or PET negative; regression to normal size on CT	Not palpable, nodules disappeared	Infiltrate cleared on repeat biopsy; if indeterminate by morphology, immunohistochemistry should be negative

Response	Definition	Nodal Masses	Spleen, Liver	Bone Marrow
PR	Regression of measurable disease and no new sites	
≥ 50% decrease in SPD of up to 6 largest dominant masses; no increase in size of other nodes
 
a FDG-avid or PET positive prior to therapy; one or more PET positive at previously involved site
 
b Variably FDG-avid or PET negative; regression on CT
	≥ 50% decrease in SPD of nodules (for single nodule in greatest transverse diameter); no increase in size of liver or spleen	Irrelevant if positive prior to therapy; cell type should be specified
SD	Failure to attain CR/PR or PD	
a FDG-avid or PET positive prior to therapy; PET positive at prior sites of disease and no new sites on CT or PET
 
b Variably FDG-avid or PET negative; no change in size of previous lesions on CT
		
Relapsed disease or PD	Any new lesion or increase by ≥ 50% of previously involved sites from nadir	
Appearance of a new lesion(s) > 1.5 cm in any axis, ≥ 50% increase in SPD of more than one node, or ≥ 50% increase in longest diameter of a previously identified node > 1 cm in short axis
 
Lesions PET positive if FDG-avid lymphoma or PET positive prior to therapy
	> 50% increase from nadir in the SPD of any previous lesions	New or recurrent involvement

a. Evaluation of Index Lesions (nodal and extranodal)

i. When index nodal lesions are not in complete response

The response for index lesions is evaluated by calculating the Sum of the Products of Diameters (SPD) of all index lesions (see Table 4-2), except when there is a Complete Response for index nodal lesions (i.e. complete normalization of all index nodal lesions) (see [Section ii.](#)).

Table 4-2 Radiological status based on SPD calculation for all index lesions

Response Criteria ¹	Evaluation of index lesions
Complete Response (CR)	See Table 4-4 below (not based on SPD calculation for all index lesions)
Partial Response (PR)	At least 50% decrease from Screening in the SPD of all index lesions
Stable Disease (SD)	Failure to attain the criteria needed for CR or PR and failure to fulfill the criteria for PD
Progressive Disease (PD)	At least a 50% increase from nadir ² in the SPD of all index lesions

¹ At each assessment (if the index nodal lesions are not in CR status), the response status based on SPD calculation will be first assessed for meeting PD status criteria, then PR status and SD status.

² Nadir is defined as the smallest sum of the product of the diameters of all index lesions recorded so far, at or after Screening.

ii. When index nodal lesions are in complete response

When there is a Complete Response for index nodal lesions (i.e. complete normalization of all index nodal lesions as defined in [Section v.](#): all index lesion ≤ 15 mm in long axis), the SPD for these index nodal lesions may not be equal to zero and therefore a calculation of a SPD for all index lesions may be misleading. Therefore, by default, a specific response for extranodal index lesions needs to be evaluated, based on the SPD calculation restricted to all index extranodal lesions only (see [Table 4-3](#)).

Table 4-3 Radiological response criteria for index extranodal lesions in case of CR in index nodal lesions

Response Criteria ¹	Evaluation of index extranodal lesions
Complete Response (CR)	Complete disappearance of all index extranodal lesions
Partial Response (PR)	At least 50% decrease from Screening in the SPD restricted to all index extranodal lesions
Stable Disease (SD)	Failure to attain the criteria needed for CR or PR and failure to fulfill the criteria for PD
Progressive Disease (PD)	At least a 50% increase from nadir ² in the SPD restricted to all index extranodal lesions

¹ At each assessment, response will be first assessed for meeting CR status. If CR status is not met, response will be assessed for PD status, then PR status and SD status.

² Nadir is defined as the smallest sum of the product of the diameters restricted to all index extranodal lesions recorded so far, at or after Screening.

The algorithm for evaluating the response integrating index extranodal lesions and the SPD calculated on all index lesions (where appropriate) provides an overall response for index lesions.

iii. Evaluation of response for all index lesions

The evaluation of response for all index lesions is based on the combination of the response for index nodal lesions (CR or non-CR), the response for index extranodal and the status based on the SPD calculated on all index lesions (nodal and extranodal), as described in Table 4-4.

Table 4-4 Radiological response for index lesions

Response for index nodal lesions ¹	Response for index extranodal lesions ¹	Status based on SPD calculation for all index lesions	Response for index lesions
CR	CR	Not calculated	CR
CR	SD/ PR	Not calculated	PR
CR	PD	PD	PD
CR	PD	PR	PR
CR	PD	SD	SD
Non-CR	Not evaluated	PD	PD
Non-CR	Not evaluated	PR	PR
Non-CR	Not evaluated	SD	SD

Response for index nodal lesions ¹	Response for index extranodal lesions ¹	Status based on SPD calculation for all index lesions	Response for index lesions
¹ If no index nodal lesions are present at Screening, then index lesions response is equal to the index extranodal lesions response. A similar rule applied if no index extranodal lesions are present at Screening, then index lesions response is equal to the index nodal lesions response.			

In case of missing measurements of any of the index lesions, the radiological response for index lesions at that assessment will be “Unknown (UNK)”, unless progression was seen.

All lesions must have been measured with the same method as the one used at Screening, otherwise the radiological response for index lesions at that assessment will be “Unknown (UNK)”.

iv. Evaluation of non-index lesions (including nodal, splenic and/or hepatic nodules and other extranodal lesions)

At each reassessment, a non-index lesion (or a group of non-index lesions) will be given one of the following designations:

- Normalization (non-index nodal lesion has regressed to normal size; non-index extranodal lesion is no longer present). Normalization of non-index nodal lesions should be determined based on their size at Screening.
- Improved, stable or worsened, but without unequivocal evidence of disease progression (non-index lesion is present but there is not sufficient worsening to declare PD based on the existing non-index lesions).
- Unequivocal evidence of disease progression (worsening of existing non-index lesions is sufficient to declare PD)
- Not assessed

Then, this status for each non-index lesion (or group of non-index lesions) will lead to a global response for non-index lesions (Table 4-5):

Table 4-5 Response criteria for non-index lesions (nodal, splenic and/or hepatic nodules and other extranodal lesions)

Response Criteria	Evaluation of non-index lesions
Complete Response (CR)	Complete normalization of all non-index nodal and extranodal lesions: Radiological regression to normal size of all lymph nodes and complete disappearance of all extranodal (including splenic and/or hepatic nodules) lesions
Stable Disease (SD)	Failure to attain the criteria needed for CR and failure to fulfill the criteria for PD
Progressive Disease (PD)	Unequivocal disease progression of any existing non-index lesions (nodal or extranodal)

In case of a missing status of any of the non-index lesions, the radiological response for non-index lesions at that assessment will be “Unknown (UNK)”, unless progression was seen.

All lesions must have been measured with the same method as the one used at Screening, otherwise the radiological response for non-index lesions at that assessment will be “Unknown (UNK)”.

v. New lesions

The appearance of

- any new nodal lesion ≥ 15 mm in any axis. New nodal lesion is defined by:
 - either a previously normal lymph node becoming > 15 mm in any axis,
 - or a previously identified abnormal lymph node showing an increase of at least 50% in the long axis,
 - as assessed by investigator

OR

- any discrete extranodal (including splenic and/or hepatic nodules) lesions reliably appearing on CT scan or MRI after Screening

is always considered as Progressive Disease (PD) and has to be recorded as a new lesion in the appropriate module of the eCRF. Determination of new lymphoma involvement in organs other than lymph nodes or liver or spleen should be confirmed histologically and the site must document that in a comment to the corresponding eCRF.

vi. Overall radiological response

Overall radiological response is calculated as shown in Table 4-6.

Table 4-6 Overall radiological response at each assessment

Index lesions	Non-index lesions ¹	New lesions	Overall radiological response
CR	CR	No	CR
CR	SD	No	PR
PR	CR or SD	No	PR
SD	CR or SD	No	SD
PD	Any	Yes or No	PD
Any	PD	Yes or No	PD
Any	Any	Yes	PD

¹If no non-index lesions are present at Screening, then this column is not used in evaluating overall radiological response.

If the evaluation of any of the index or non-index lesions identified at Screening could not be made during follow-up or if the index or non-index response is “Unknown (UNK)”, the overall response status at that assessment must be “Unknown (UNK)” unless progression or a new lesion was seen.

vii. Evaluation of overall disease response

The evaluation of overall disease response at each assessment is a composite of the individual radiological responses (index and non-index lesions, new lesions), laboratory test (bone marrow) and clinical responses (lymphoma related clinical symptoms).

viii. Bone marrow re-assessment at time of radiological CR

In order to confirm a Complete disease response (CR), bone marrow biopsy or aspirate may be required when a radiological CR has been achieved. Details are provided in the Study Protocol. The infiltrate of lymphoma in bone marrow must have cleared on repeat bone marrow biopsy or aspirate. Patients who achieve a CR by other criteria but who have persistent morphologic positive or inconclusive bone marrow involvement will be considered partial responders. New or recurrent bone marrow involvement anytime during the follow up will be considered PD. Bone marrow biopsy or aspirate will be performed after the first assessment of CR or when clinically indicated.

The biopsy sample of bone marrow must be adequate (with a goal of > 20 mm unilateral core). If the sample is indeterminate by morphology, it should be negative by immunohistochemistry.

ix. Overall disease response

If a patient has an overall radiological response of CR then this response must be confirmed by bone marrow biopsy or aspirate (if required as per the Study Protocol), presence of normal liver and spleen size, and evaluation of lymphoma related B-symptoms. The patient's overall response will be calculated as follows:

A patient will be deemed to have overall disease response of CR if bone marrow biopsy or aspirate becomes negative for tumor involvement (if the bone marrow was involved by lymphoma at Screening) and the liver and spleen are normal in size and there are no lymphoma related B-symptoms in addition to radiological CR.

If assessments of any of the following: lymphomatous infiltration of bone marrow (If required as per the Study Protocol), or evaluation of B-symptoms is not done, unknown or indeterminate or B-symptoms are still present when the overall radiological response is assessed as CR or the liver or spleen are enlarged, then the overall disease response will be assessed as PR until evaluation of these factors have shown normalized results and recorded on the corresponding eCRF.

For patients whose radiological response is anything other than CR, assessment of bone marrow, liver, spleen and B-symptoms will not be required in evaluating overall response and overall disease response is the same as radiological response. However any new or recurrent bone marrow involvement at any time during follow-up will be considered PD.

Of note, appearance of B-symptoms or enlarged spleen or liver will not in themselves constitute documentation of progression. They are however expected to be associated with progressive disease. Every effort should be made to document that evidence radiologically and report the corresponding tumor assessments. Such tumor assessments are expected to be performed within 2 months of appearance of B-symptoms or enlarged spleen or liver.

5. References (available upon request)

Cheson BD (2007a) The international harmonization project for response criteria in lymphoma clinical trials. Hematol Oncol Clin N Am 21:841-854.

Cheson BD (2009) The case against heavy PETing. *J Clin Oncol* 27:1742-1743.

Cheson BD, Pfistner B, Juweid ME, et al (2007b) Revised response criteria for malignant lymphoma. *J Clin Oncol* 25:579-586.

FDA Guideline (2005) Clinical Trial Endpoints for the Approval of Cancer Drugs and Biologics, April 2005.

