10.4 Primary objective

The primary objective is to assess the clinical benefit of treatment with PDR001 + LAG525 at 24 weeks of treatment based on local investigator assessment.

For patients with solid tumors, the assessment criteria will be RECIST 1.1 and will include responses of CR or PR or SD. For lymphoma the Revised Response Criteria for Malignant Lymphoma (Cheson et al 2007) criteria will apply. Response criteria are included in the appendices.

For solid tumors, an assessment of CR or PR using RECIST 1.1 must be confirmed at least 4 weeks after initial observation. If the two assessments differ, the best overall response will be determined by Table 14-3 of [Appendix 1](#).

For efficacy parameters, data will be listed, summarized, or analyzed by tumor cohort.

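### In DLBCL, Appendix 2 Table 4-4 scores normalised index nodes plus stable extranodal disease as PR without calculating the all-index SPD, while Table 4-1 requires a fall of at least 50%; the tables must be reconciled before ORR is reported

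*Protocol*

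**What the plan says.** All references are to Protocol Appendix 2 (the lymphoma criteria) unless stated.

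- **Measurability (section 2a).** "For nodal lesion, if the long axis is > 15 mm, regardless of the length of the short axis". Patients are expected to have "at least one measurable nodal lesion greater than 20 mm", but there is a second way in: "In cases where the patient has no measurable nodal lesions greater than 20 mm in the long axis at Screening", a measurable extranodal lesion suffices. Inclusion criterion 4 has the same route.
- **Normalisation (section 2c).** "A measurable nodal lesion must become ≤ 15 mm in long axis to be considered normalized". No minimum change is required.
- **PR in general.** Table 4-1 asks for an SPD fall of at least 50% in nodal masses, and the same for liver and spleen nodules. Whatever misses CR and PR and is not PD is SD. Table 4-2, the status based on all index lesions, sets PR at "At least 50% decrease from Screening in the SPD of all index lesions".
- **PR after nodal CR (section 4a iii, Table 4-4).** Nodal CR with extranodal SD or PR is one row. Its result is PR, and the all-index SPD is marked as not calculated. The three rows for nodal CR with extranodal PD do use the all-index SPD.
- **Carry-through (Table 4-6).** Index PR with non-index CR or SD and no new lesion is overall PR.
- **Confirmation (Protocol 10.4).** "For solid tumors, an assessment of CR or PR using RECIST 1.1 must be confirmed at least 4 weeks after initial observation". SAP 2.5.2 likewise limits confirmation to solid tumours. The extra lymphoma checks (marrow, liver and spleen, B symptoms, PET) apply to CR only.

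**The concern.** Measurability and normalisation meet at the same 15 mm line, so a 1 mm change in one small node can produce nodal CR. The Table 4-4 row then turns that into PR, whatever the extranodal disease has done short of PD. The same patient is SD under Table 4-1. Two tables in one appendix therefore give different answers for patients who have both nodal and extranodal index lesions.

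At stake is the DLBCL ORR, which SAP 2.7.2 reports separately for each haematological tumour type (listing only below 4 patients). TTR and DOR are exposed too, because they run to or from the first documented response. One misclassified patient moves ORR by 1/24 = 4.2 points in a cohort of 24 and by 1/10 = 10 points in a cohort of 10.

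**Working it through.** **1. The rules, as applied below**

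- Nodal CR: all index nodes at or below 15 mm.
- SPD status: PD if at least 1.5 times nadir, PR if at most 0.5 times Screening, otherwise SD.
- The status is taken over extranodal lesions for Table 4-3 and over all index lesions for Table 4-2. Nadir equals Screening in the examples.

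Section 4a i exempts the nodal-CR case from Table 4-2. The direct conflict is therefore with Table 4-1; Table 4-2 shows what the uncalculated column of Table 4-4 would have said.

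**2. Worked records**

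*Node 16x12 to 15x12, mass 50x40 to 57x52*
- Extranodal: 57x52 = 2964 against 2000, +48%, SD.
- All index: 192 + 2000 = 2192 to 180 + 2964 = 3144, +43%.
- Table 4-4: **PR**. Table 4-1, and the Table 4-2 status: **SD**.

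*Same record, node still read as 16 mm*
- No nodal CR, so the all-index SPD decides: 192 + 2964 = 3156, +44%, **SD**. One millimetre on the small node is the whole difference.

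*Same record, node 15x12, mass 57x53*
- Extranodal: 3021 against 2000, +51%, PD. The all-index SPD is now used: 180 + 3021 = 3201, +46%, **SD**.

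*Usual entry route: node 21x14 to 15x10, extranodal 30x30 unchanged*
- 294 + 900 = 1194 to 150 + 900 = 1050, -12.1%. Table 4-4: **PR**. The shrinkage is real but well short of 50%, so the conflict does not depend on measurement error.

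**3. How often noise alone could trigger the row**

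The documents give no measurement error, so this is an illustration. Assumptions: one index node read 16-20 mm at screening, no true change, true sizes spread evenly over 10-26 mm, independent normal errors, readings rounded to 1 mm, scans at weeks 12, 18 and 24, extranodal disease stable. A false PR is any reading at or below 15 mm.

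The first column holds every patient progression-free to week 24. The second counts only scans before progression, using the protocol's own DLBCL figure of 3 months median PFS, exponential. That assumption reproduces the stated historical CBR: 0.5^(6/3) = 25%. At weeks 12, 18 and 24 (2.76, 4.14 and 5.52 months) it leaves 0.5^(t/3) = 53%, 38% and 28% progression-free.

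| Measurement SD (mm) | All progression-free | 3-month exponential PFS |
|---|---|---|
| 0.75 | 15% | 7% |
| 1.0 | 21% | 9% |
| 1.5 | 31% | 14% |
| 2.0 | 39% | 17% |

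With two index nodes, both of which must read at or below 15 mm, the first column falls to 2-11%. A node above 20 mm must lose more than 25% of its long axis, so noise matters little there.

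**The case against.** **The row has a reason.** Section 4a ii explains that normalised nodes keep a non-zero size, so an all-index SPD can mislead after nodal CR. That is fair, and using it has a price: a node 40x20 to 15x15 with a stable 20x20 extranodal lesion goes from 1200 to 625, -47.9%, and becomes SD although all nodal disease has normalised. But the appendix relies on this same SPD in the nodal-CR/extranodal-PD rows, so the reason does not explain why only the SD case omits it. Large nodal responses survive: 50x40 to 15x10 with a stable 20x20 lesion is 2400 to 550, -77%.

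**Response is the local investigator's call, and Table 4-1 is where the response definitions are listed.** An investigator following it would not call the worked record PR. That is true, but the result then depends on which table was followed, which is the reason to reconcile them.

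**The route is narrow.** This stands. It needs nodal and extranodal index lesions together. A patient with no index node takes the extranodal response directly (Table 4-4, footnote 1). Appendix 2 does not require every measurable node to be an index lesion; if a small node is non-index and normalises, Table 4-6 gives SD.

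**Growth is bounded.** Also true. A reader might infer that any growing tumour can score as a response. In this row extranodal growth is capped below 50% from nadir, and a new lesion or non-index PD still overrides.

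**Conclusion.** The contradiction stands on the text and needs no assumption about measurement error: nodal CR plus extranodal SD is PR by Table 4-4, and SD by Table 4-1 unless SPD falls by at least 50%. The fault lies in the Table 4-4 row. The 15 mm cut-point only makes the row easy to reach.

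The reach is limited. A reader might infer that the primary endpoint or the go/no-go decisions are affected. They are not, because CBR counts SD as benefit. What remains is descriptive: DLBCL ORR and TTR, and DOR, which SAP 2.7.2 pools over all tumour types. The DLBCL cohort is capped at 24 in the primary population and 30 in all.

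The 7-17% is a per-patient illustration for one index node of 16-20 mm, given the assumed measurement SD of 0.75-2.0 mm. The 15-39% also requires every patient to be progression-free through week 24, which contradicts the protocol's PFS assumption. A reader might turn either range into a cohort-wide ORR inflation. The documents do not support that, because they give neither the share of patients entering by the extranodal route nor the number of index nodes per patient.

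This should be corrected before a DLBCL ORR is reported. It does not threaten the trial's main conclusion.

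**What to change.** Split the second row of Table 4-4:

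- nodal CR + extranodal PR: PR;
- nodal CR + extranodal SD: decided by the all-index SPD, as in the nodal-CR/extranodal-PD rows. PR if it has fallen at least 50% from Screening, otherwise SD.

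State that the new SD row can return only PR or SD. A node may grow from 5x5 mm (the small-lesion default in section 3a ii) to 15x15 mm, 25 to 225 mm², and still count as normalised. An all-index PD driven by such nodes would change progression, and with it CBR, which this correction should leave alone.

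Derive DLBCL ORR, TTR and DOR on this rule from lesion sizes already collected, and report beside them the number of responders under the present row. Since the SAP addendum records post-database-lock changes, label the re-derivation as post hoc and show both counts.

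Cost: one table row and one derivation, with no new data. DLBCL ORR may be slightly lower, and some patients whose nodes normalise but whose total SPD falls just short of 50% (the -47.9% case above) will move from PR to SD.
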